## 5 SELECTION AND EXCLUSION OF PATIENTS FOR THE STUDY

### 5.16 Inclusion criteria to be met by study participants

- Invasive mechanical ventilation for an expected duration of at least 48 hours
- Nutritional support started within 24 h after intubation
- Treatment with a vasoactive amine (adrenaline, dobutamine, or noradrenaline) via a central venous catheter
- Age older than 18 years
- Informed about the study and having consented to participation in the study
- Covered by the French public health insurance system

### 5.17 Noninclusion criteria to be absent in study participants

- Invasive mechanical ventilation started more than 24 h earlier
- Patient admitted for an acute gastrointestinal condition that contraindicates enteral nutrition
- Surgery on the gastrointestinal tract within the past month
- History of gastrectomy, esophagectomy, duodenopancreatectomy, bypass surgery, gastric banding, or short bowel syndrome

---

- Gastrostomy or jejunostomy
- Specific nutritional needs, such as pre-existing long-term home enteral or parenteral nutrition
- Active gastrointestinal bleeding
- Dying patient – not-to-be-resuscitated order or other treatment-limitation decision at ICU admission
- Adult under guardianship
- Pregnancy, recent delivery, or lactation
- Department of corrections inmate
- Institutionalized patient
- Prior inclusion in a randomized trial designed to compare enteral and parenteral nutrition
- Contraindication to parenteral nutrition: known hypersensitivity to egg or soybean proteins or to another component, inborn error in amino-acid metabolism, or severe familial dyslipidemia affecting triglyceride levels

### 5.3 Recruitment modalities

Participation in the study will be suggested to all patients admitted to the study ICUs, given vasoactive amine therapy, placed under invasive mechanical ventilation for an expected duration of at least 48 h, and requiring early enteral or parenteral nutritional support.

### 5.4 Contraindication to participation in another research project

Patients included in this study will not be eligible for participation in other studies that compare enteral and parenteral nutrition and/or that have the same objectives.

### 5.5 Critères d'inclusion des personnes qui se prêtent aux études ancillaires

Patients meeting the criteria for inclusion in the NUTRIREA2 trial will be eligible for inclusion in the ancillary studies, after the patient, a relative, or a surrogate receives information and states that he/she has no objection to inclusion in the ancillary studies (see the specific patient information document in the appendix).

## 6 PRODUCTS ADMINISTERED TO THE STUDY PARTICIPANTS

### 6.1 Study intervention

We will evaluate two strategies for initiating nutritional support: first-line parenteral nutrition and first-line enteral nutrition. Patients allocated at random to the enteral-nutrition group (E) will receive enteral nutrition only; and those allocated at random to the parenteral-nutrition group (P group) parenteral nutrition only for at least 72 hours and until day 7 of invasive mechanical ventilation, except if the physician in charge decides that the clinical situation mandates continued parenteral nutrition. In both groups, nutritional support will be started within 24 h after intubation. The selection of nutritional preparations will be at the discretion of the investigators according to availability and standard protocols used in each ICU.

The daily calorie target in both groups is 20-25 Kcal/Kg/day at the acute phase of ICU management, in compliance with current recommendations (4-6, 77). This calorie intake is adequate in over 90% of ICU patients with systemic insults and equals 1.3- to 1.5-fold the mean resting energy expenditure (REE) estimated using simplified equations. In addition, this calorie intake avoids overnutrition, which may induce deleterious effects (metabolic and hepatobiliary complications) (77-79).

In the enteral-nutrition group (E group), the patients will receive first-line enteral nutrition. In the event of persistent intolerance precluding achievement of the calorie targets, supplemental parenteral nutrition may be added starting on day 8 (6, 72).

In the parenteral-nutrition group (P group), the course of action will be guided by the hemodynamic evaluations conducted daily starting 72 hours after parenteral nutrition initiation and until day 7. A stable hemodynamic status is defined for this study as discontinuation of the vasoactive amines and a normal level of arterial lactic acid (<2 mmol/L). As soon as these two criteria are met, the patient will be switched from parenteral to enteral nutrition, in the absence of absolute contraindications to the enteral route. The calorie targets and mode of nutritional-support initiation are identical to those in the early enteral-nutrition group (E group). Starting on D8, in patients without contraindications to enteral feeding, the enteral route will be substituted for the parenteral route.

After extubation, regardless of the time since randomization, decisions about the continued need for, and optimal route of, nutritional support will be at the discretion of the physician in charge of the patient.

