NONINCLUSION CRITERIA FOR STUDY PARTICIPANTS	
 
▪ invasive mechanical ventilation started more than 24 hours earlier
 
▪ surgery on the gastrointestinal tract within the past month
 
▪ history of gastrectomy, esophagectomy, duodenopancreatectomy, gastric bypass or banding, or short bowel syndrome
 
▪ gastrostomy or jejunostomy
 
▪ specific diet
 
▪ active bleeding from the gastrointestinal tract
 
▪ dying patient – not-to-be-resuscitated order or other treatment limitation decision at ICU admission
 
▪ adult under guardianship
 
▪ pregnancy, recent delivery, or lactation
 
▪ patient admitted without his or her consent
 
▪ department of corrections inmate
 
▪ institutionalized patient
 
▪ prior inclusion in a randomized trial comparing early enteral nutrition to early parenteral nutrition and having mortality as the primary outcome measure
 
▪ contraindication to parenteral nutrition: known hypersensitivity to egg protein, soybean protein, or another component; inborn error in
 

	amino acid metabolism; severe familial dyslipidemia manifesting as hypertriglyceridemia
STRATEGIES / PROCEDURES	In both groups, nutritional support will be started within 24 hours after the initiation of mechanical ventilation. Calorie targets will be 20-25 Kcal/Kg/day during the first week then 25-30 Kcal/Kg/day starting on day 8. In the parenteral nutrition group, a switch to the enteral route will be possible after at least 72 hours of parenteral nutrition, provided the vasoactive agent(s) were stopped at least 24 hours earlier and the arterial lactic acid level is lower than 2 mmol/L; on day 7, all patients will be switched to enteral nutrition in the absence of an absolute contraindication to use of the enteral route. In the enteral nutrition group, supplemental parenteral nutrition may be added, starting on day 8, in patients with intolerance to enteral nutrition and inadequate calorie intakes. A written protocol for prescribing and delivering nutritional support will be available to ensure standardization across study centers.

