#### 4.2.4 Study intervention: first-line enteral or parenteral nutrition

After study inclusion, patients will be allocated at random to one of two nutritional-support strategies (Figure 1).

[figure not shown]
**In the parenteral-nutrition group (P group),** the patients will receive first-line parenteral nutrition for at least 72 hours. After these 72 hours, the course of action will depend on the results of the daily hemodynamic status evaluation. If the hemodynamic condition is stable (no vasoactive amines for 24 consecutive hours and arterial lactic acid level below 2 mmol/L) and the enteral route can be used, parenteral nutrition will be stopped and immediately replaced by enteral nutrition at the flow rate needed to achieve the previously defined calorie target. If on the contrary the patient still requires vasoactive amine therapy and/or the arterial lactic acid level is equal to or greater than 2 mmol/L, parenteral nutrition will be continued for a total of 7 days (168 hours). On day 8, in the absence of contraindications to enteral nutrition, parenteral nutrition will be stopped and enteral nutrition started. Supplemental parenteral nutrition may be added subsequently in the event of intolerance to enteral nutrition precluding the achievement of the predefined calorie targets.

**In the enteral-nutrition group (E group),** the patients will receive first-line enteral nutrition. In the event of persistent gastrointestinal intolerance precluding achievement of the

---

predefined calorie targets, supplemental parenteral nutrition may be added starting on day 8 in compliance with North-American recommendations and with the recently published study by Casaer (6, 72). Isoosmotic isocaloric normal-protein polymeric preparations will be used during the first week, after which the choice of the preparation will be at the discretion of the physician. To minimize the risk of gastric intolerance and consequently of vomiting, the volume of supplemental water given enterally will be as small as possible during the first study week.

Figure 1: Protocol

---

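### The rule that ends first-line parenteral nutrition in the parenteral group is stated in contradictory ways in the synopsis, section 4.2.4 and section 6.1

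*Combined protocol and SAP*

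**What the plan says.** Three places give the rule for leaving parenteral nutrition in the P group.

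- **Synopsis, Strategies / procedures.** The early switch is permissive: "a switch to the enteral route will be possible after at least 72 hours of parenteral nutrition". Its condition is "provided the vasoactive agent(s) were stopped at least 24 hours earlier and the arterial lactic acid level is lower than 2 mmol/L". The latest time is given as "on day 7, all patients will be switched to enteral nutrition in the absence of an absolute contraindication".
- **Section 4.2.4.** After 72 hours, a stable patient is one with "no vasoactive amines for 24 consecutive hours and arterial lactic acid level below 2 mmol/L". If the enteral route is usable, parenteral nutrition is then stopped and replaced at once. A patient who still needs amines, or whose lactate is 2 mmol/L or more, continues to a total of 168 hours. Then: "On day 8, in the absence of contraindications to enteral nutrition, parenteral nutrition will be stopped and enteral nutrition started".
- **Section 6.1.** The first paragraph gives parenteral nutrition alone for at least 72 hours and up to day 7 of invasive ventilation, "except if the physician in charge decides that the clinical situation mandates continued parenteral nutrition". The last paragraph sets out daily haemodynamic evaluations from 72 hours and gives a study definition of stability with two parts: amines discontinued, and lactate below 2 mmol/L. It contains no 24-hour period. It continues: "As soon as these two criteria are met, the patient will be switched from parenteral to enteral nutrition", absent an absolute contraindication, with substitution of the enteral route from D8 for the rest.

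The overview of benefits and risks (2.2 in the table of contents) adds that the single modality lasts between 72 hours and 7 days.

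**The concern.** These are bedside instructions in an open trial at 28 centres, and for some patients they conflict. Take a patient at the 72-hour evaluation whose amines stopped 12 hours earlier and whose lactate is normal. Section 6.1 requires the switch. The synopsis condition is not met. Section 4.2.4 does not place the patient at all: its stable branch needs 24 amine-free hours, and its other branch covers only those still on amines or with raised lactate. Section 6.1 cannot easily be read as shorthand for the fuller rule, because it presents its wording as the study's definition and counts the criteria as two.

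How long parenteral feeding continues after the 72-hour minimum is part of the strategy given to the parenteral group. If centres follow different sections, that strategy varies by centre, and there is no single standard against which to call a patient adherent. The synopsis says a written protocol will ensure standardization across centres, and the overview of benefits and risks counts standardization as a benefit to patients.

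**Working it through.** The plan gives no figure for this rule, so there is nothing to reproduce. The check is a comparison of texts, followed by the hours that follow from them.

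**Step 1. Texts side by side**

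| Element | Synopsis | 4.2.4 | 6.1 |
|---|---|---|---|
| Minimum | 72 h | 72 h | 72 h |
| Lactate | below 2 mmol/L | below 2 mmol/L | below 2 mmol/L |
| Time off amines | at least 24 h | 24 consecutive h | none stated |
| Early switch | optional | mandatory | mandatory in last paragraph; absent from the first-paragraph sentence on duration |
| Latest time | day 7 | after 168 h, on day 8 | until day 7 of ventilation (first paragraph); from D8 (last paragraph) |
| Exception | absolute contraindication | enteral route not usable, or contraindication | contraindication, plus a physician decision to continue |

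The minimum and the lactate threshold agree. The amine-free period and the status of the switch do not. The two paragraphs of 6.1 also differ from each other. The clock is not fixed either: 4.2.4 counts hours of parenteral nutrition, the first paragraph of 6.1 counts days of ventilation, and the study population description (2.4 in the contents) defines the acute phase by days in the ICU.

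**Step 2. Hours of parenteral nutrition under 6.1 and 4.2.4**

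Assumptions: evaluations at 72, 96, 120 and 144 h from the start of parenteral nutrition; a cap at 168 h; lactate below 2 mmol/L throughout; no contraindication; amines not restarted; patient still ventilated. Section 4.2.4 is read as re-applied at each daily evaluation, so a patient with fewer than 24 amine-free hours waits for the next one.

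Let *t* be the hour at which amines stop.

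- Under 6.1, parenteral nutrition ends at the first evaluation at or after *t*, otherwise at 168 h.
- Under 4.2.4, it ends at the first evaluation at or after *t* + 24, otherwise at 168 h.

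| Amines stop at *t* | 6.1 | 4.2.4 | Difference |
|---|---|---|---|
| 24 h or 48 h | 72 h | 72 h | 0 |
| 60 h | 72 h | 96 h | 24 h |
| 96 h | 96 h | 120 h | 24 h |
| 120 h | 120 h | 144 h | 24 h |
| 144 h | 144 h | 168 h | 24 h |
| 150 h | 168 h | 168 h | 0 |

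The two sections therefore differ by 24 h for 48 h < *t* ≤ 144 h and agree outside that range. Relative to the 6.1 duration, the gap runs from 24/72 = 33% at the short end to 24/144 = 17% at the long end.

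**Step 3. Optional against mandatory**

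If the switch is only possible, as in the synopsis, a patient stable at 72 h could receive anything from 72 h to about 168 h, a range of up to 168 − 72 = 96 h. Under 4.2.4 or 6.1 the same patient stops at 72 h.

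**The case against.** The case on the other side is substantial and limits the point in several ways.

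- **Day 7 against day 8.** A reader might infer a further 24-hour conflict. The documents do not support that. The follow-up flowchart in 4.2.7 starts at D0, which runs from inclusion to midnight, so 168 hours after inclusion falls on D7; counted from day 1, the end of 168 hours is the start of day 8. The two labels may mean the same moment. Even if they do not, the gap does not add to the 24 hours above, because a given patient stops either by the haemodynamic rule or at the cap.
- **Exceptions.** It would be wrong to say that 4.2.4 has none: it allows for contraindications and an unusable enteral route. The physician exception in 6.1 is broader, and that difference stands.
- **Primary analysis.** A reader might infer that the main comparison is compromised. It compares first-line strategies by randomized group, no per-protocol population is defined, and randomization is stratified by site, so each centre's parenteral patients have enteral controls from the same centre. No bias or loss of power is shown.
- **Ancillary studies.** Citrulline at H72 falls within the 72-hour minimum common to all versions, and the aspirates of the first 48 hours precede any switch. Only later samples, chiefly the secondary D8 assays, follow a route history that depends on the rule used.
- **Visibility.** Section 4.6 records daily volumes and calories, catecholamine use and lactate, so actual exposure can be described. Catecholamines are recorded only as yes or no per day, however, so the amine-free interval is not captured to the hour.
- **Unseen material.** Figure 1 is not shown, and the synopsis promises a written nutrition protocol. Either might give one rule, so actual divergence between centres is not established. Neither removes the contradiction in the protocol text.

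What remains is the 24-hour criterion, the optional or mandatory status, the internal disagreement in 6.1, the exception wording and the unfixed clock.

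**Conclusion.** The contradiction is real and lies in the protocol's operative text. Under the stated assumptions, 6.1 ends parenteral nutrition 24 hours earlier than 4.2.4 for patients whose amines stop after 48 h and up to 144 h, and at the same time for everyone else. The optional wording in the synopsis allows a wider spread. The share of patients in that range is not given, and no effect on day-28 mortality can be computed.

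The consequence is limited to the consistency of the parenteral strategy between centres, any statement about adherence, and the secondary D8 assays. The intention-to-treat primary analysis, the H72 citrulline endpoint and the 48-hour aspirates stand. It should be corrected because the instructions conflict for the same patient and correction is cheap, not because the trial's main inference is in doubt.

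**What to change.** Reconcile the synopsis, the overview of benefits and risks, 4.2.4 and both paragraphs of 6.1 so that the same four items appear throughout:

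1. one set of switch criteria, worded so that every patient falls under exactly one branch, including those whose amines stopped less than 24 hours earlier;
2. one status for the switch, mandatory or optional;
3. one clock with a stated origin, and one latest time on it;
4. one statement of exceptions.

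Check that Figure 1 and the written nutrition protocol match, and notify the centres. Which criteria, status, time and exceptions to adopt is a clinical decision for the investigators. The cost is a wording amendment and a note to centres; sample size, randomization and the planned analyses do not change.

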## 6.2 Treatments that may be used

All the medications whose use is standard practice for ICU patients will be used according to the specific needs of each patient.

## 6.3 Treatments that may not be used

Given that this study evaluates standard care, no medication used according to its marketing authorization is contraindicated.

---

## 7 STATISTICS

The statistical analysis will be carried out at the CIC INSERM 202 under the responsibility of [name]. The analyses will be performed using SAS 9.2 and R software.

### 7.1 Description of planned statistical methods, with the schedule of planned interim analyses

The statistical analysis will be conducted according to a predefined plan. The analysis will follow the intention-to-treat (ITT) approach, as recommended for superiority studies. Two interim analyses will be performed, given the need for a large number of included patients. A statistical analysis report will be written to describe all the findings to be communicated, according to CONSORT Statement recommendations, while taking into account the specific features of the trial, i.e., the nonpharmacological nature of the intervention (<http://www.consort-statement.org/>).

#### 7.1.1 Description of the groups at baseline

The groups established by randomization will be compared using descriptive statistics. No statistical tests will be performed.

#### 7.1.2 Analysis populations

The ITT approach will be used: each patient will remain in the group assigned by randomization, regardless of subsequent events.

#### 7.1.3 Analysis of the primary endpoint

Day-28 mortality will be reported as the point estimate with the 95% confidence interval in each group. Day-28 mortality will be compared between the two groups using the chi-square test.

---

#### 7.1.4 Analysis of secondary endpoints

- For the analysis of patients with at least one nosocomial infection,
  - we will use a competitive-risk model, with death as the competing risk, since patients who have died cannot experience nosocomial infections;
  - in addition, the proportion of patients having at least one nosocomial infection will be analyzed in the same way as the primary endpoint, in order to obtain a sensitivity analysis of observed results.
- VAP
  - proportion of patients with at least one VAP episode: the method used will be the same as for nosocomial infections, with not only death as a competing risk, but also time to extubation +2 days, since after this point any episode of pneumonia would not be classified as a VAP episode;
  - VAP incidence density as the point estimate with the 95% confidence interval;
  - number of VAP episodes per patient analyzed using a negative binomial regression model with no offset variable
- Bacteremia, central venous catheter (CVC)-related infections, urinary tract infections, soft tissue infections: each of these categories of infection will be analyzed using the same method as for the pooled nosocomial infections
- Descriptive bacteriological data (organisms recovered with their resistance profiles for each nosocomial infection): only descriptive analyses will be performed
- Proportion of patients with at least one episode of vomiting or regurgitation: the method will be the same as for the primary analysis
- Proportion of patients with at least one episode of diarrhea: the method will be the same as for the primary analysis
- Proportion of patients with at least one episode of constipation: the method will be the same as for the primary analysis
- Proportion of patients with at least one documented episode of acute pseudoobstruction of the colon (Ogilvie syndrome): the method will be the same as for the primary analysis
- Proportion of patients with at least one documented episode of bowel ischemia: the method will be the same as for the primary analysis
- Proportion of patients with at least one mechanical complication of CVC insertion: the method will be the same as for the primary analysis

- Proportion of patients with at least one episode of CVC obstruction or other dysfunction requiring a change of CVC: the method will be the same as for the primary analysis
- The number of calories delivered each day by the enteral and parenteral routes: changes over time in delivered calories will be represented graphically by boxplots created each day on the same graph; changes over time will be compared between the two groups using a mixed linear model, after data transformation if necessary
- Volume of enteral and parenteral feeds delivered each day: the analysis method will be the same as for the number of calories
- Ratio of prescribed over delivered calories: the proportions of patients who achieved their daily calorie target will be determined at each follow-up time point (in days) and will be compared between the two groups using a logistic random effects model
- ICU mortality, 90-day mortality, and hospital mortality: day-90 mortality will be analyzed in the same way as day-28 mortality; for ICU and hospital mortality rates, competing-risk models will be used, as ICU discharge and hospital discharge compete with death during the stay
- Nutritional markers and body weight: changes over time in nutritional markers and body weight will be analyzed using the method described above for the number of calories delivered
- Proportion of patients with at least one episode of liver dysfunction: the method will be the same as for the primary objective
- Times in the ICU, in the hospital, and on mechanical ventilation will be compared between the two groups using nonparametric Wilcoxon tests

